### **Safety and Monitoring:**

**Assessment of Side Effects:** Significant side effects are defined as changes > 30% from baseline in the mean arterial pressure, HR, or oxyhemoglobin pulse oximetry < 90. Any unexpected or serious side effects will be reported to the IRB within 24 hrs.

Peripheral oxyhemoglobin saturation, BP and HR will be measured non-invasively before and 15, 30, 60, 120, 180, 240, minutes after intravenous oxytocin injection. If either BP or HR change by > 30%, or oxyhemoglobin saturation decreases to less than 90, and require treatment, these vital signs will be repeated at 5-minute intervals until vital signs are stabilized.

**Treatment of Side Effects:** Mean blood pressure elevations greater than 30% of baseline will be treated with labetalol 5-15 mg IV incrementally until BP elevation is less than 30% elevated. Reductions in mean BP > 30% of baseline will be treated with incremental ephedrine 5-20 mg, IV. Heart rate (HR) reductions or elevations > 30% of

baseline will be treated with incremental glycopyrrolate 0.2 mg IV or propranolol 0.2 mg IV, respectively. Peripheral oxyhemoglobin desaturation (< 90) will be treated with supplemental oxygen, nasal cannula, face mask, or non-rebreathing mask depending upon the degree desaturation and the response to therapy.

## **RISKS**

Risks of intravenous cannulation include pain on insertion and bruising at the site. Risks from the FDA approved heat stimulus device are pain, and the subject can stop testing at any time if the pain they perceive is such that they do not want to continue. Please note that these devices are used in many pain clinics routinely and have multiple fail-safe designs to avoid thermal burn. Risks from the non-regulatory vibratory device are related only to microshock and are addressed in the Appendix.

Risks of oxytocin are primarily restricted to uterine contraction in the presence of pregnancy, since oxytocin receptors are not present in the non-pregnant uterus (Package insert attached).

Additionally there is the possibility of a feeling of being flushed, headache and increased heart rate with no significant change in blood pressure during or immediately after the infusion. These events have been reported by previous participants but were short lived, lasting approximately 12-15 minutes.

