## Protocol

### Pharmacokinetics of intravenous oxytocin and effects on sensory function in healthy volunteers

**PRIMARY GOAL:** Measure oxytocin in plasma after brief intravenous infusion and model its pharmacokinetics.

**METHODS:** Equal numbers of healthy adult men and women will be recruited (ten total). At least 1 day prior to study subjects will be trained to rate pain in response to heat applied to the lateral calf using a Peltier controlled thermode and to indicate when they first perceive a vibratory stimulus on the fingertips and wrist.

Subjects will return for study visit two in which an intravenous catheter will be inserted in the arm and, after baseline measures of response to heat and determination of vibration frequency threshold, subjects will receive oxytocin (Pitocin®), 10 IU over 10 minutes. Venous blood samples (5 ml) will be obtained before and at 2, 5, 10, 15, 30, 45, 60, 90, 120, 180, and 240 minutes after the end of the oxytocin administration by removal of blood from the intravenous catheter.

We will abandon an individual participant's study and schedule another participant should we be unable to successfully place the intravenous catheter.

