## **STUDY DESIGN**

**Inclusion Criteria:** We request permission to study up to 12 subjects so that we will have 10 evaluable subjects with complete sampling at all time periods.

1. Male or female  $\geq 18$  and  $\leq 60$  years of age, Body Mass Index (BMI)  $<40$ .
2. Generally in good health as determined by the Principal Investigator based on prior medical history, American Society of Anesthesiologists physical status I or II
3. Normal blood pressure (systolic 90-140 mmHg; diastolic 50-90 mmHg) resting heart rate 45-100 beats per minute) without medication
4. Female subjects of child-bearing potential and those  $< 1$  year post-menopausal, must be practicing highly effective methods of birth control such as hormonal methods (e.g., combined oral, implantable, injectable, or transdermal contraceptives), double barrier methods (e.g., condoms, sponge, diaphragm, or vaginal ring plus spermicidal

jellies or cream), or total abstinence from heterosexual intercourse for a minimum of 1 full cycle before study drug administration.

Exclusion Criteria:

1. Hypersensitivity, allergy, or significant reaction to any ingredient of Pitocin®
2. Any disease, diagnosis, or condition (medical or surgical) that, in the opinion of the Principal Investigator, would place the subject at increased risk (active gynecologic disease in which increased tone would be detrimental e.g., uterine fibroids with ongoing bleeding), compromise the subject's compliance with study procedures, or compromise the quality of the data
3. Women who are pregnant (positive result for serum pregnancy test at screening visit), women who are currently nursing or lactating, women that have been pregnant within 2 years
4. Subjects with neuropathy, chronic pain, diabetes mellitus, or taking benzodiazepines or pain medications on a daily basis.

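### RISKS and exclusion 2 rest on opposite premises about the non-pregnant uterus, and no symptom question is scheduled on the dosing day

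*Combined protocol and SAP*

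**What the plan says.** All references are to the combined protocol and SAP.

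- **RISKS.** The section states that "Risks of oxytocin are primarily restricted to uterine contraction in the presence of pregnancy" and gives as the reason that "oxytocin receptors are not present in the non-pregnant uterus". It refers to an attached package insert. It then adds: "Additionally there is the possibility of a feeling of being flushed, headache and increased heart rate". It places these events during or just after the infusion and says that earlier participants had them for about 12-15 minutes.
- **STUDY DESIGN, exclusion 2.** Among the conditions that the Principal Investigator may judge to raise a subject's risk, it gives "active gynecologic disease in which increased tone would be detrimental e.g., uterine fibroids with ongoing bleeding".
- **STUDY DESIGN, exclusion 3.** Pregnant women, nursing women and women pregnant within the past 2 years are excluded separately.
- **Safety and Monitoring.** "Significant side effects are defined as changes > 30% from baseline in the mean arterial pressure, HR, or oxyhemoglobin pulse oximetry < 90". Saturation, blood pressure and heart rate are measured before dosing and at 15, 30, 60, 120, 180 and 240 minutes after it. Unexpected or serious side effects go to the IRB within 24 hours.
- **Long-term Follow-up.** Volunteers are contacted daily in the following week and asked about adverse events.
- **HUMAN SUBJECTS.** All risks are to be discussed with each volunteer.

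**The concern.** The protocol gives two incompatible accounts of whether oxytocin can act on the uterus of a woman who is not pregnant. The eligibility criteria treat the effect as a reason not to dose some women. The risk text gives a reason why it should not occur. The risk discussion promised under HUMAN SUBJECTS needs one consistent list to draw on.

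The monitoring plan has a related gap. It schedules three physiological measurements on the dosing day and no enquiry about how the participant feels. That leaves out any uterine symptom, and also flushing and headache, which RISKS itself expects.

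The study is meant to support later work. BACKGROUND describes computer-controlled infusions over a wide concentration range. The Data Safety Monitoring Plan already draws reassurance from earlier intranasal studies that described no adverse events. A tolerability record from this study obtained without asking about symptoms could be read in the same way.

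**Working it through.** The plan gives no figure to reproduce on this point. The check is a comparison of passages with a little arithmetic.

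**1. Whom exclusion 2 can affect.** Exclusion 3 already removes pregnant women. Any woman kept out only by the gynecologic example in exclusion 2 is therefore not pregnant. The example is uterine and the stated hazard is increased tone, so it presumes that oxytocin could raise tone in a non-pregnant uterus. The receptor clause in RISKS has no qualifier and denies the mechanism. The two rest on opposite premises.

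**2. Number of women dosed.** The METHODS text plans ten participants with equal numbers of men and women: 10 / 2 = 5 women. The Inclusion Criteria ask for up to 12: 12 / 2 = 6 women, assuming the equal split is kept.

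**3. Timing of the transient symptoms.** Inputs: a 10-minute infusion (METHODS), onset during or just after it and duration about 12-15 minutes (RISKS), first check at 15 minutes (Safety and Monitoring). Count from the start of infusion and take onset between 0 and 10 minutes.

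- Earliest end of symptoms: 0 + 12 = 12 minutes. Latest end: 10 + 15 = 25 minutes.
- The monitoring text does not say whether its 15 minutes run from the start or the end of the infusion.
- If from the end, the first check falls at 10 + 15 = 25 minutes. All such symptoms would be over by then or just ending.
- If from the start, it falls at 15 minutes. Symptoms that began at 0 would end at 12-15 minutes, by the time of the check. Symptoms that began at 10 would end at 22-25 minutes and still be present.

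On either reading, the check as written records only saturation, blood pressure and heart rate.

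**4. What the plan captures for each effect.**

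| Effect | Scheduled on dosing day | In the definition of significant side effects | First stated enquiry |
|---|---|---|---|
| Increased heart rate | Yes, six post-dose times | Yes, if change exceeds 30% | Dosing day |
| Flushing | No | No | Follow-up contacts, general question |
| Headache | No | No | Follow-up contacts, general question |
| Uterine symptom | No | No | Follow-up contacts, general question |

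The IRB rule covers unexpected or serious effects once they are known. It does not provide for anyone to ask. Flushing and headache are named in advance, so when not serious they fall outside that rule as well.

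**The case against.** The strongest reply has five parts.

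- **Disclosure.** A reader might infer that women are not told of a uterine risk, or are told that it is absent. The documents do not support this. The consent form and package insert are not available for review, and HUMAN SUBJECTS promises discussion of all risks. Only the omission from RISKS can be shown. This part stands.
- **Collection.** A reader might infer that uterine effects would go uncollected or that there is nowhere to record them. That is also too strong. The daily contacts ask openly about adverse events. The IRB rule is not limited by organ system, and on the RISKS premise a uterine effect in a non-pregnant woman would itself be unexpected. No case report form is in the documents. This part stands too; what remains is that no dosing-day question and no uterine item are specified.
- **The contradiction is soft.** RISKS says that the risks are primarily, not wholly, confined to pregnancy. Exclusion 2 is a precaution left to the investigator's opinion, for women with active disease who are not dosed. This has some force, but the hedge does not reach the receptor clause, which is stated without exception for diseased tissue and is given as the reason.
- **No stated uterine symptom.** No passage says that oxytocin may cause cramping or bleeding in non-pregnant women. In exclusion 2 the bleeding is a feature of the existing disease. This stands, so the risk wording cannot be supplied from the documents alone.
- **Small stakes.** The study gives one 10-minute dose to 5 or 6 women, and BACKGROUND does not say that later infusions will be longer. This stands, and it keeps the point modest.

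**Conclusion.** The point holds in limited form. The receptor statement in RISKS and the gynecologic example in exclusion 2 conflict and must be reconciled; the documents do not settle which premise is right. RISKS names no uterine effect for the women dosed. Of the three non-uterine effects it does name, only heart rate is measured on the dosing day. Flushing, headache and any uterine symptom wait for general questioning in the following week, unless a participant volunteers them or staff notice them.

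This affects risk text and tolerability data. It does not touch the primary outcome, which STATISTICAL RATIONALE defines as plasma oxytocin concentration. The conclusion assumes that the monitoring section is the full schedule of dosing-day safety assessments, since no data form is available to show otherwise. The change is worth making because it is cheap and the symptoms are short-lived.

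**What to change.** 1. Reconcile RISKS with exclusion 2 against the attached package insert, so that the risk text and the exclusion rest on the same premise. Carry the agreed wording into the risk discussion under HUMAN SUBJECTS.
2. At the vital-sign times already listed in Safety and Monitoring, and at the Long-term Follow-up contacts, add one fixed symptom question covering flushing, headache and, in women, uterine symptoms. Record onset and end times, so that an episode that is over before the first check is still recovered.

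The cost is a revised sentence of risk text and one extra line on a form, at times when staff are already with or in touch with the participant. The risk statement may become less favourable. Dose, blood sampling and sample size do not change.

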## **HUMAN SUBJECTS**

All studies in volunteers will be performed in the CRU, which includes monitoring and resuscitation equipment and trained nursing support staff, or in in-patient settings of the Wake Forest Baptist Medical Center. All studies will be approved by the IRB and written informed consent obtained. The Project Investigators have all performed similar studies in volunteers and patients. The purpose of the study and all risks will be discussed with each volunteer, and all questions will be answered prior to obtaining written informed consent. Risks to be discussed include discomfort with needle and catheter insertion. All data acquired will remain confidential with no reference to individuals in publications.

## **Data Safety Monitoring Plan**

Although the use of oxytocin in this protocol is outside FDA approval for oxytocin administration during labor or in the postpartum period, the dose to be studied is similar to or less than that of multiple recent studies in healthy volunteers with intranasal oxytocin purchased over the counter in the US [4-7; 9-21] and without description of adverse events. For these reasons, we do not propose a data safety monitoring committee or special safety evaluation beyond those required by IRB regulations.

## **Minority, Gender, and Children Participation**

Both sexes and races and ethnicities will be actively recruited in this small study. Children under age 18 are not included in these protocols because this protocol because the safety of this product has not been established in children.

## **Volunteer Payment**

Participants will be paid a total of \$300 according to the following payment schedule which we have used throughout the last 2 cycles of this grant's protocols. We believe that this payment schedule is fair and appropriate, paying for each procedure attempted and an additional payment for completion of the entire study.

Completion of study 1: \$25

Placement of IV: \$25

Completion of entire study: \$250

Volunteer must complete all of the above phases to receive this payment.

## **Long-term Follow-up**

Volunteers will be contacted daily within the following week and questioned about adverse events from the study.

## **STATISTICAL RATIONALE**

**Primary outcome measure** is the concentration of oxytocin in plasma at defined times after intravenous infusion. We request a convenience sample of 10 subjects for the purpose of preliminary data to provide variance estimates that will inform federal grant

submission for use of the pharmacokinetic parameters from this sample or proposal of a larger sample size to adequately characterize such parameters.

